7.4.3 Week 1, Day 1 (Dose 1)

Pre-dose:

1. Subject self-completes the CFQ-R prior to all other procedures and assessments
2. Symptom directed physical examination (including body weight)
3. Vital signs
4. Oximetry
5. Concomitant medications review
6. AE review
7. Administer any routine pulmonary medications and airway clearance techniques, including SABA and/or LABA, Pulmozyme, inhaled corticosteroids and/or antibiotics
8. Initiate continuous cardiac and vital signs monitoring and continue for 12 hours post dose
9. Spirometry (FEV₁, FVC, and FEF₂₅₋₇₅), post administration of short-acting bronchodilator
10. Obtain blood samples for local laboratory assessments
11. Obtain urine sample for urinalysis (Time 0/pre-dose)
12. Obtain blood and urine samples for PK (Time 0/pre-dose)

Study Drug Administration:

Study drug to be administered by qualified site personnel via the designated study nebulizer, until all study drug solution has been administered. Subjects are to be seated during the entire

duration of study drug administration, inhaling the nebulized study drug using normal tidal breathing (no noseclips). Details regarding study drug preparation, device preparation and handling, as well as administration of study drug will be included in the Pharmacy Manual and Study Manual.

Post-dose:

1. Symptom-directed physical examination at 15, 60 minutes, 2, 4, 6, 8, and 12 hours post dose
2. Vital signs at 1, 10, 30, 60 minutes, 2, 4, and 12 hours post dose
3. Oximetry at 1, 10, 30, 60 minutes, 2, 4, and 12 hours post dose
4. Concomitant medications review
5. AE review
6. Spirometry at 10, 30, and 60 minutes, and 2, 4, and 8 hours post dose
7. Obtain blood samples for local laboratory assessments at 30, 60 minutes, 2, 4, 8, and 12 hours post dose
 - Complete blood count (CBC) with absolute differential
 - Serum chemistry
8. Obtain the following samples for PK:
 - Blood at 0.5, 1, 2, 3, 4, 12 hours post dose
 - Pooled urine from 0 to 4 hours and 4 to 12 hours post dose. Subjects should empty their bladders just prior to dosing and at the end of each time interval for the final urine collection of that interval. Urinalysis by dipstick will be performed on the pooled urine samples for each time interval.
 - Sputum at 3 times post dose, within the first 6 hours post dose. Suggest obtaining samples in conjunction with performing spirometry at 10, 60 minutes, and 4 hours post dose.
9. Discharge subject

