7.4.9 Week 4 (Dose 12)

Pre-dose:

1. Complete physical examination (including body weight)
2. Vital signs
3. Oximetry
4. Concomitant medications review
5. AE review
6. Obtain blood and urine samples for PK prior to dosing
7. Administer any routine pulmonary medications and airway clearance techniques, including SABA and/or LABA, Pulmozyme, inhaled corticosteroids and/or antibiotics
8. Spirometry (FEV₁, FVC, and FEF₂₅₋₇₅)
9. Administer study drug

Post-dose:

1. Symptom-directed physical examination within 2 hours post dose
2. Vital signs within 2 hours post dose
3. Oximetry within 2 hours post dose
4. Spirometry at 20, and 60 minutes, 4 hours post dose
5. Obtain the following samples for PK:
 - Blood at 1, 2, 3, 4, and 8 hours post dose
6. Obtain sample for sweat chloride determination

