13.8 Pharmacokinetics Analyses

To determine the PK profile of inhaled administrations at the different dose levels of QR-010, the following PK parameters will be calculated if sufficient data are available for each dose:

- C_{max} : The maximum serum concentration will be taken directly from the data.
- T_{max} : Time to C_{max} will be taken directly from the data.
- $T_{1/2}$: The terminal elimination half-life will be estimated by non-linear regression analysis of the terminal elimination slope, if feasible.
- AUC_{0-t} : Area under the curve to the final sample with a concentration greater than lower limit of quantification (LLQ) will be calculated using the linear trapezoidal method.
- $AUC_{0-\infty}$: Area under the curve to infinity will be calculated based on the last observed concentration $C_{last}(obs)$ using formula: $AUC_{0-\infty} = AUC_{last} + C_{last}(obs)/\lambda_z$, if feasible.
- CL: Serum clearance will be estimated using the formula: $CL = Dose/AUC_{0-\infty}$.

Achievement of steady state of the drug will be determined from trough levels.

Exact procedure for imputation of data will be described in the SAP.

All samples obtained from all cohorts will be analyzed to avoid bias in data presentation.

Sparse sampling analysis may be used to mitigate the risk of insufficient data to create individual profiles. The same approach may be used for non-compartmental analysis of sputum concentrations. This option provides the opportunity to characterize drug PK in CF patients as thoroughly as possible while keeping blood draws to a reasonable minimum for ethical considerations.

Correlation between concentrations in different matrices (serum, urine, sputum) may be explored.

Drug concentrations will be summarized by nominal time point if 3 or more values are available. Descriptive statistics for PK parameters will be performed if $\geq 50\%$ of subjects have evaluable data and number of values to summarize is ≥ 3 .

Geometric means and coefficients of variation will be tabulated for C_{\max} , AUC_{0-t} , $AUC_{0-\infty}$ and CI for each dose group if possible. T_{\max} will be summarized by median, minimum and maximum. Mean, standard deviation, minimum and maximum will be provided for $T_{1/2}$. Exact details for statistical analysis of PK concentrations and derived PK parameters will be presented in SAP.

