| C-Reactive Protein | X | | | | |
| Erythrocyte Sedimentation Rate | X | | | | |
| C-Reactive Protein & Erythrocyte Sedimentation Rate | Dose 10: Pre-dose | | | | |
| Urine microalbumin | X | | | | |
| Urinalysis | Dose 10: Urine microalbumin pre-dose Dose 10: Urinalysis pre-dose, 60 minutes and 2 hours post dose | | | | |
| Sweat Chloride | | | | | X |
| PK Sampling | Serum: Pre-Dose 10 and 11; Dose 12 (pre-dose; post dose at 1, 2, 3, 4, 8 hours) Urine: Dose 12 pre-dose only | | | | |
| Serum for PK | X | | X | | X |
| Urine for PK | | | | | X |
| Biomarker Sampling | Dose 10: Pre-dose | | | | |
| Blood (serum and plasma) for Biomarkers | X | | | | |
| Sputum for Biomarkers | X | | | | |

Table A.2-6: Multiple Ascending Dose Cohorts 5-8, Follow-up

| Study Procedures | PK Follow-up 24 hours After Last Dose | PK Follow-up 96 Hours After Last Dose | 7 Days After Last Dose (End of Treatment) ^a | 28 Days After Last Dose (End of Study) ^a |
|-----------------------------------------|------------------------------------------------------------------------------------------------------------------------------------------------------------------------------------|---------------------------------------------|-----------------------------------------------------------------|-----------------------------------------------------------|
| Study Day | 27 | 30 | 33 | 54 |
| In Hours Post Dose 1 | 624 ± 12 | 696 ± 96 | 768 | 1272 |
| Hematology | | | X | X |
| Serum Chemistry | | | X | X |
| C-Reactive Protein | | | X | |
| Erythrocyte Sedimentation Rate | | | X | |
| Coagulation and CH50 | | | X | |
| Direct Antibody Test | | | X | |
| Urine microalbumin | | | | X |
| Urinalysis | | | X | X |
| Pregnancy test ^b | | | X | X |
| Sputum for Microbiology | | | X | |
| Sweat Chloride | | | X | X |
| PK Sampling | Serum post last dose: 24 ±12 hrs, 96 ± 48, hours post last dose, and at End of Treatment and End of Study Visit Urine post last dose: 24 ±12 hrs, 96 ± 48, hours post last dose | | | |
| Serum for PK | X | X | X | X |
| Urine for PK | X | X | | |
| Biomarker Sampling | End of Treatment and End of Study Visits | | | |
| Blood (serum and plasma) for Biomarkers | | | X | X |
| Sputum for Biomarkers | | | X | X |

^a See Section 5.5.2 for details on these visits for subjects who withdraw prematurely from the study.

^b Women of child-bearing potential only

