#### **4.9. Pharmacokinetic Evaluations**

In the SAD portion of the study, sample collections for support of PK analysis are planned as follows:

- Blood (i.e. serum): pre-dose (time 0), 0.5, 1, 2, 3, 4, 12, 24, 48, 54, 72, 168 hours post-dose.
- Urine: Pre-dose (time 0); Pooled from 0 to 4, 4 to 12, and 12 to 24 hours post-dose; and 48, 72, and 168 hours post dose.
- Sputum: 3 samples obtained within first 6 hours post dose; 24 hours post dose; Day 4 (72 hours post dose); and Day 8 (168 hours post dose)

In the MAD portion of the study, sample collections for support of PK analysis are planned as follows:

Week 1, Dose 1

- Serum: 0, 0.5, 1, 2, 3, 4, 12; pre-Dose 2 (48 hours post-dose 1)
- Urine: Pre-dose; Pooled from 0 to 4 and 4 to 12 hours post Dose 1.
- Sputum: pre-dose, 3 samples obtained within first 6 hours post Dose 1.

Week 4, Dose 12

- Serum: pre-dose (0), 1, 2, 3, 4, 8, 24, 96, 144 (7 days post-last dose) and 648 hours (28 days post-last dose).
- Urine: Pre-dose; 24 and 96 hours, post-dose.

Additional sample collections are planned on interim study days during the MAD portion of the study. The measured concentrations will be presented in listings and used to confirm adequate QR-010 exposure; however, they will not be used to support generation of PK parameters. Additionally, urine concentrations that did not come from pooled collections or for which sample volumes were not collected will only be displayed in listings and will not be used to support generation of renal PK parameters.

The planned PK parameters for each portion of the study may be found in Table 26 below. Area under the serum concentration curve (AUC) will be generated using the linear-log trapezoidal rule.

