**Table 26: Planned Pharmacokinetic Parameters by Matrix and Study Day**

Parameter	Definition	Calculation
SAD, Study Day 1, Serum PK Parameters		
C max	Maximum serum concentration	Observed
T max	Time of maximum serum concentration	Observed
AUC last	Area under the concentration-time curve from 0 to the last quantifiable serum concentration	Linear-Log trapezoidal method
AUC inf	Area under the concentration-time curve from 0 extrapolated to infinite	Calculated as AUC 0-last + C est,last /λ z , where C est,last is the estimated last measurable concentration
T 1/2	Apparent terminal elimination half-life	ln(2)/λ z , where λ z is the apparent first-order terminal elimination rate constant.
λ z	Terminal elimination rate constant	Log-linear regression of the concentration-time curve during terminal elimination
Cl/F	Apparent Clearance	Dose/AUC inf
V d /F	Apparent volume of distribution	Dose/AUC inf * λ z
SAD, Study Day 1, Urine PK Parameters		
A e	Amount excreted unchanged in the urine	Cumulative: Sum of concentration* volume per collection interval
Fe%	Fraction of Dose excreted	Calculated as A e /Dose, where A e is the amount of unchanged drug excreted in urine during a collection

	unchanged in the urine	interval and D is the Dose
Clr	Renal Clearance	Calculated as $Ae_{24}/AUC_{24}$ where Ae is the amount of unchanged drug excreted in urine during the first 24 hours post-dose and $AUC_{24}$ is the Area under the concentration versus time curve from 0 to 24 hr.
MAD, Week 1, Dose 1, Serum		
Cmax	Maximum serum concentration	Observed
Tmax	Time of maximum serum concentration	Observed
AUCtau	Area under the concentration-time curve from 0 to the end of the dosing interval (tau, where tau will equal 48 hours).	Linear-log trapezoid
MAD, Week 4, Dose 12, Serum		
Ctrough	Trough serum concentration	Observed
Cmax	Maximum serum concentration	Observed
Tmax	Time of maximum serum concentration	Observed
AUCtau *	Area under the concentration-time curve from 0 to the end of the dosing interval (tau, where tau will equal 48 hours).	Linear-log trapezoid
Css	Steady-state concentration	$AUC_{tau}/tau$ , where tau will equal 48 hours

Ro	Accumulation ratio	AUCtau (week 4, dose 12)/ AUCtau (week 1, dose 1)
Ro,Cmax	Cmax, accumulation ratio	Cmax(week 4, dose 12)/ Cmax (week 1, dose 1)

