Accumulation Index	Estimated accumulation index	$1/(1 - e^{-\lambda * \text{tau}})$
CL/F	Apparent clearance	Dose/AUCtau
V/F	Apparent volume	Dose/AUCtau* $\lambda z$

\*Sampling collection scheme during week 4, dose 12 allows for sample collection windows. The 96-hr sample time collection may occur between 48 and 144 hours post dose. For samples in which C48 was collected, AUCtau will be generated using observed data. For samples in which C48 was not collected, C48 will be estimated using each subject's individually estimated  $\lambda$  from week 4, dose 12, provided there is sufficient data to estimate the elimination rate constant. Data will be considered sufficient if there are no less than 3 time points included in the estimation, R-squared values are at least 0.9, and the percent of data extrapolated is less than 20%.

Concentrations below the limit of quantification (BQL) will be considered to be 0 concentration. With the possible exception of C48 (week 4, dose 12), missing values will not be imputed. If sufficient data are missing for a given subject, that subject may be considered non-evaluable for pharmacokinetic analysis and will not be included in the PK Population.

All serum, urine and sputum concentration data and the per-subject pharmacokinetic parameters will be displayed in listings. Summary statistics will be generated for each pharmacokinetic parameter unless there are less than three subjects will evaluable data. Summary statistics will include mean, median, geometric mean, standard deviation, minimum, maximum, and percentage of coefficient of variation. Concentration-time profiles will be plotted by individual and mean concentration-time profiles will be plotted by dose and study day on both the log and linear scales (if applicable). Dose-normalized parameters will be plotted for dose-ranging studies. Because there may be a relationship between pseudomonas and QR-010 systemic exposure, summary statistics and descriptive figures may also be generated by day, dose and pseudomona at the discretion of the team, but no formal statistical analysis will be performed and these additional tables and figures will be excluded from the top line report.

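### The Cmax accumulation ratio in SAP Table 26 compares maxima from two different serum sampling grids, so it can read low if the peak is very early and high if it is late (minor)

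*SAP*

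**What the plan says.** SAP section 4.9 lists the MAD dose-1 serum samples as "Serum: 0, 0.5, 1, 2, 3, 4, 12; pre-Dose 2 (48 hours post-dose 1") and the dose-12 samples as "Serum: pre-dose (0), 1, 2, 3, 4, 8, 24, 96, 144" hours, with one later sample. The Protocol has the same difference: section 7.4.3 gives "Blood at 0.5, 1, 2, 3, 4, 12 hours post dose" for dose 1, section 7.4.9 gives "Blood at 1, 2, 3, 4, and 8 hours post dose" for dose 12, and Appendix 2 repeats the latter as "Dose 12 (pre-dose; post dose at 1, 2, 3, 4, 8 hours"). The difference is therefore part of the design and not a slip in the SAP.

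SAP Table 26 takes Cmax as the observed value on each day, in line with Protocol section 13.8: "The maximum serum concentration will be taken directly from the data". It defines the Cmax accumulation ratio as "Cmax(week 4, dose 12)/ Cmax (week 1, dose 1"). Nothing limits the two maxima to shared sampling times.

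Nothing else in the plan fills the gap. Apart from a possible estimate of the 48 h concentration at dose 12, "missing values will not be imputed". Section 4.9 also keeps the interim-day samples out of the PK parameter calculations.

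**The concern.** An observed maximum depends on when blood is drawn. A peak at 0.5 h can be recorded at dose 1 but cannot be recorded at dose 12, where the first post-dose sample is at 1 h. A subject with identical profiles on both days would then have a ratio below 1 purely because of the sampling times.

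An early peak cannot be ruled out in advance. SAP section 4.7 expects nebulization to take less than about 20 minutes, a 0.5 h sample is planned both in the SAD part and at MAD dose 1, and Protocol section 2.1.4 states that there is no earlier clinical experience with the product.

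The grids also differ later in the day. Dose 12 has an 8 h sample, whereas dose 1 has none between 4 and 12 h. A late peak can be caught at dose 12 and missed at dose 1, which pushes the ratio up.

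At stake is how a summarised PK parameter is read: a value below 1 would be taken as absence of accumulation, or a late-peak value as more accumulation than there is.

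**Working it through.** The documents state no accumulation ratio, Tmax or half-life, so there is no planned figure to reproduce. All kinetic values below are assumptions, shown as a range.

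**Inputs from the documents**
- Dose-1 grid: 0, 0.5, 1, 2, 3, 4, 12, 48 h (SAP 4.9; Protocol 7.4.3).
- Dose-12 grid: 0, 1, 2, 3, 4, 8, 24, 96 h (SAP 4.9; Protocol 7.4.9 and Appendix 2). Later samples do not affect the maximum.
- Times common to both: pre-dose, 1, 2, 3, 4 h.
- Monday-Wednesday-Friday dosing, with dose 12 at 600 h after dose 1 (Protocol 7.1 and Table A.1-5).

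**Early peak, short half-life.** Assume one compartment with first-order absorption: C(t) proportional to exp(-ke·t) - exp(-ka·t), with ke = ln 2 / half-life and ka chosen so that Tmax = ln(ka/ke)/(ka - ke). For half-lives of 4 h or less almost nothing is left after 48 h (at 4 h, 2^(-48/4) = 0.0002), so the true ratio is 1.000. With the peak at 0.5 h or earlier, the highest dose-1 sample is at 0.5 h and the highest dose-12 sample is at 1 h. The planned ratio is then

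C(1)/C(0.5) = exp(-ke/2) + exp(-ka/2) = 2^(-0.5/half-life) + exp(-ka/2).

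| Tmax | Half-life | ka (per h) | Planned ratio | True ratio |
|---|---|---|---|---|
| 0.5 h | 1 h | 4.38 | 0.707 + 0.112 = 0.819 | 1.000 |
| 0.5 h | 2 h | 6.07 | 0.841 + 0.048 = 0.889 | 1.000 |
| 0.5 h | 4 h | 7.78 | 0.917 + 0.020 = 0.937 | 1.000 |
| 0.25 h | 1 h | 12.15 | 0.707 + 0.002 = 0.709 | 1.000 |
| 0.25 h | 2 h | 15.57 | 0.841 + 0.000 = 0.841 | 1.000 |
| 0.25 h | 4 h | 18.95 | 0.917 + 0.000 = 0.917 | 1.000 |

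The simple factor 2^(-0.5/half-life) alone describes a peak near 0.25 h. For a peak at 0.5 h it overstates the fall, because absorption is still going on.

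**Early peak, long half-life.** Adding up all 12 doses, for a 0.5 h peak the planned ratio is 1.307 against a true 1.324 (half-life 24 h), and 1.908 against 1.921 (48 h). Since 1.307/1.324 = 0.987 and 1.908/1.921 = 0.993, the bias is about 1%.

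**Peak at about 0.75 to 4 h.** Planned and true ratios agree to about 0.1%.

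**Late peak.**

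| Tmax | Half-life | True | Planned | Common-time |
|---|---|---|---|---|
| 6 h | 8 h | 1.023 | 1.047 | 1.029 |
| 8 h | 8 h | 1.032 | 1.128 | 1.054 |
| 8 h | 24 h | 1.358 | 1.424 | 1.457 |
| 8 h | 48 h | 1.962 | 2.011 | 2.122 |

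The planned ratio is 2 to 9% too high (1.047/1.023 = 1.02; 1.128/1.032 = 1.09).

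**Fast distribution with a slow terminal phase.** Assume 90% of the concentration declines with a 1 h half-life, 10% with a 48 h half-life, and absorption has a half-life of 0.1 h. Dose 1 gives 0.704 at 0.5 h and 0.548 at 1 h. Dose 12 gives 0.638 at 1 h, carry-over included. The planned ratio is 0.638/0.704 = 0.906 against a true 1.127, and the common-time ratio is 0.638/0.548 = 1.17.

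**Effect of using common times.** For one-compartment peaks at 0.25 to 0.5 h, the ratio from pre-dose, 1, 2, 3 and 4 h is within 0.1% of the true ratio at every half-life tried (0.5 to 48 h).

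**The case against.** The strongest reply is that little depends on this ratio. PK is a secondary objective, accumulation is not named among the objectives, and escalation and the MTD rest on DLTs and adverse events. Table 26 also gives an AUC-based ratio, trough concentrations and an estimated accumulation index, and Protocol 13.8 judges steady state from troughs. Tmax is reported for both days, and all concentrations are listed, so a dose-1 peak at 0.5 h would be visible. All of this stands and keeps the point minor. It does not remove the mismatch: the ratio is still planned and summarised without a caution. The AUC-based ratio also has different sampling over the first hour; that effect was not calculated.

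A second reply is that where the bias is large there is hardly any accumulation to hide. In the one-compartment model this is right: biases of 6% or more for a 0.5 h peak occur at half-lives of 4 h or less, where the true ratio is 1.000. Real accumulation reads as a decline only with a profile such as the two-phase one above, which is possible but assumed.

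A third reply concerns the remedy. A 1 to 4 h ratio is not a Cmax ratio, and for an 8 h peak with a 24 or 48 h half-life it is further from the truth than the planned ratio. That stands, and is why it should be added and not substituted.

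A reader might infer that the error can only go downward, the unsafe direction. The grids do not support that, because the extra 8 h sample at dose 12 biases the ratio upward for late peaks.

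**Conclusion.** The point holds as a conditional one. That the grids differ, and that Table 26 ignores it, is certain from the documents. Whether it matters depends on Tmax and on the decline after the peak, neither of which the documents give. In the one-compartment model, for half-lives of 1 to 4 h, the ratio is about 6 to 18% too low if the peak is at 0.5 h and about 8 to 29% too low if it is at 0.25 h. It is about 1% too low when the half-life is 24 to 48 h, unaffected for peaks at about 0.75 to 4 h, and 2 to 9% too high for peaks at 6 to 8 h.

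It would be going too far to say that the trial will understate accumulation, or that a main question of the MAD part is compromised. The Protocol describes that part as assessing safety, tolerability and exploratory efficacy, and Ro,Cmax feeds no decision rule. Importance: minor.

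**What to change.** In SAP Table 26:
- Keep full-grid Cmax and Tmax for each day, and the planned Ro,Cmax.
- Add a second, clearly labelled common-time ratio: the highest dose-12 concentration over the highest dose-1 concentration, using only the nominal times pre-dose, 1, 2, 3 and 4 h on both days.
- Report by dose group how many subjects have dose-1 Tmax at 0.5 h.
- State in advance that the common-time ratio is the one to rely on when dose-1 peaks fall at 0.5 h, and that it can overstate accumulation if peaks fall after 4 h.

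The cost is one extra descriptive parameter and a few lines of text. No new samples are needed. The price in interpretation is that the added ratio is not a true Cmax ratio, so the label must say so.

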^b Includes FEV₁, FVC, and FEF₂₅₋₇₅.

^c See Appendix 2 for a detailed schedule of these assessments, broken down by type of specimen and time relative to dose.

^d Subjects who are taking concurrent CF therapy should receive this therapy prior to study drug dosing in the order specified in Section 6.3.1.

Table A.1-4: Multiple Ascending Dose Cohorts 5-8, WEEK 3

| Study Procedures | Dose 7 | | Dose 8 | | Dose 9 | | |
|----------------------------------------|--------|-----|--------|-----|--------|-----|-----|
| Study Day | 15 | 16 | 17 | 18 | 19 | 20 | 21 |
| In Hours Post Dose 1 | 336 | 360 | 384 | 408 | 432 | 456 | 480 |
| Concomitant Medications | X | | X | | X | | |
| Adverse Events | X | | X | | X | | |
| Physical Exam | C/S | | S | | S | | |
| Height & Weight | W | | | | | | |
| Vital Signs ^a & Oximetry | X | | X | | X | | |
| Spirometry ^b | X | | | | | | |
| CFQ-R RSS ^c | X | | | | | | |
| Blood for Safety Labs ^d | X | | | | | | |
| Urinalysis ^d | U | | | | | | |
| Biomarkers ^d | X | | | | | | |
| Study Drug Administration ^e | X | | X | | X | | |
| Collect Samples for PK ^d | X | | X | | X | | |

Abbreviations: C = complete physical exam; CFQ-R RSS = Cystic Fibrosis Questionnaire-Revised Respiratory Symptom Score; PK = pharmacokinetic; S = symptom-directed physical exam; U = urinalysis (dipstick); W = weight

NOTE: See also Section 7.4 for details on timing of assessments relative to study drug administration.

^a Includes blood pressure, heart rate, respiratory rate, and temperature.

^b Includes FEV₁, FVC, and FEF₂₅₋₇₅.

^c Should be completed prior to any other procedures or assessments.

^d See Appendix 2 for a detailed schedule of these assessments, broken down by type of specimen and time relative to dose.

^e Subjects who are taking concurrent CF therapy should receive this therapy prior to study drug dosing in the order specified in Section 6.3.1.

Table A.1-5: Multiple Ascending Dose Cohorts 5-8, WEEK 4

| Study Procedures | Dose 10 | | Dose 11 | | Dose 12 |
|--------------------------------------------------|---------|-----|---------|-----|---------|
| Study Day | 22 | 23 | 24 | 25 | 26 |
| In Hours Post Dose 1 | 504 | 528 | 552 | 576 | 600 |
| Concomitant Medications | X | | X | | X |
| Adverse Events | X | | X | | X |
| Physical Exam ^a | C/S | | S | | C/S |
| Height & Weight | W | | | | W |
| Vital Signs ^b & Oximetry ^a | X | | X | | X |
| Spirometry ^{a,c} | X | | | | X |
| Blood for Safety Labs ^d | X | | | | |

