| Urinalysis ^d | U | | | | |
| Biomarkers ^d | X | | | | |
| Sweat Chloride ^d | | | | | X |
| Study Drug Administration ^e | X | | X | | X |
| Collect Samples for PK ^d | X | | X | | X |

Abbreviations: C = complete physical exam; PK = pharmacokinetic;

S = symptom-directed physical exam; U = urinalysis (dipstick); W = weight

^a See Section 7.4 for details on timing of these assessments relative to study drug administration.

^b Includes blood pressure, heart rate, respiratory rate, and temperature.

^c Includes FEV₁, FVC, and FEF₂₅₋₇₅.

^d See Appendix 2 for a detailed schedule of these assessments, broken down by type of specimen and time relative to dose.

^e Subjects who are taking concurrent CF therapy should receive this therapy prior to study drug dosing in the order specified in Section 6.3.1.

Table A.1-6: Multiple Ascending Dose Cohorts 5-8, Follow-Up Visits

| Study Procedures | PK Follow-up 24 Hours After Last Dose | PK Follow-up 96 Hours After Last Dose | 7 Days After Last Dose (End of Treatment) | Follow-up 28 Days after Last Dose (End of Study) |
|--------------------------------------|---------------------------------------------|---------------------------------------------|----------------------------------------------------|-----------------------------------------------------------|
| Study Day | 27 ± 1 | 30 ± 2 | 33 | 54 |
| In Hours Post Dose 1 | 624 ± 12 | 696 ± 48 | 768 | 1272 |
| Concomitant Medications | | | X | X |
| Adverse Events | | | X | X |
| Physical Exam | | | C | C |
| Height & Weight | | | W | W |
| Vital Signs ^a & Oximetry | | | X | X |
| Spirometry ^b | | | X | X |
| Chest Xray | | | X | |
| 12-lead ECG | | | X | |
| CFQ-R RSS ^c | | | X | X |
| Blood for Safety Labs ^d | | | X | X |
| Urinalysis ^d | | | U | U |
| Pregnancy test ^{d,e} | | | X | X |
| Sputum for Microbiology ^d | | | X | |
| Biomarkers ^d | | | X | X |
| Sweat Chloride ^d | | | X | X |
| Collect Samples for PK ^d | X | X | X | X |

Abbreviations: C = complete physical exam; CFQ-R RSS = Cystic Fibrosis Questionnaire-Revised Respiratory Symptom Score; PK = pharmacokinetic; U = urinalysis (dipstick); W = weight

^a Includes blood pressure, heart rate, respiratory rate, and temperature.

^b Includes FEV₁, FVC, and FEF₂₅₋₇₅.

^c Should be completed prior to any other procedures or assessments.

^d See Appendix 2 for a detailed schedule of these assessments, broken down by type of specimen and time relative to dose.

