**Table 5: Target Visit/Days for MAD**

Dose (Visit)	Expected date EXPDATE (Dose n-1 date + expected number of days)	Target Dose Visit Date
Dose 1 (Day 1)	Day 1	Dose 1 date
Dose 2 (Day 3)	Dose 1 date + 2 days (i.e. 3-1), time 00:00	
 
• If any dose within expected date +/-1 days then = this dose date,
 
• else = expected date (i.e. = Dose 1 date + 2 days)
 

Day 4	Day 3 Target date+1 day	Day 3 Target date+1 day
Dose 3 (Day 5)	Day 3 Target date + 2 days (5-3), time 00:00	
 
• If any dose within expected date +/-1 days then = this dose date,
 
• else = expected date (i.e. Day 3 Target Date + 2 days)
 

Dose 4 (Day 8)	Day 5 Target date + 3 days (8-5), time 00:00	"
Dose 5 (Day 10)	Day 8 Target date + 2 days, time 00:00	"
Dose 6 (Day 12)	Day 10 Target date + 2 days, time 00:00	"
Dose 7 (Day 15)	Day 12 Target date + 3 days, time 00:00	"
Dose 8 (Day 17)	Day 15 Target date + 2 days, time 00:00	"
Dose 9 (Day 19)	Day 17 Target date + 2 days, time 00:00	"
Dose 10 (Day 22)	Day 19 Target date + 3 days, time 00:00	"
Dose 11 (Day 24)	Day 22 Target date + 2 days, time 00:00	"
Dose 12 (Day 26)	Day 24 Target date + 2 days, time 00:00	"
Day 33	Day 26 Target date + 7 days	Day 26 Target date + 7
Day 54	Day 26 Target date + 28 days	Day 26 Target date + 28

For time points with time precision relative to dose (i.e. "Dose time+ XX min"), the time is computed with respect to the end time of dosing (end of inhalation).

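### SAP 4.9 labels the 7- and 28-day dose 12 serum samples 24 hours too early, and departs from named PK rules in protocol 13.8 while SAP Section 5 reports no changes

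*SAP*

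**What the plan says.** **Time labels.** The dose 12 serum list in SAP 4.9 runs 0, 1, 2, 3, 4, 8, 24 and 96 h and ends with "144 (7 days post-last dose) and 648 hours (28 days post-last dose"). The SAD serum list in the same section is "0.5, 1, 2, 3, 4, 12, 24, 48, 54, 72, 168 hours post-dose", where the last entry is the Day 8 sample, 7 days after the dose. SAP Table 5 sets Day 33 at "Day 26 Target date + 7 days" and Day 54 at "Day 26 Target date + 28 days". On the protocol's clock of hours after dose 1, the week 4 row of Table A.1-5 is "504 | 528 | 552 | 576 | 600", with dose 12 in the last column. The follow-up row of Table A.1-6 is "624 ± 12 | 696 ± 48 | 768 | 1272". The SAP's own copies of these tables carry the same values.

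**Use of nominal times.** Protocol 13.8: "Drug concentrations will be summarized by nominal time point if 3 or more values are available". SAP 4.9, in the text after Table 26: "mean concentration-time profiles will be plotted by dose and study day on both the log and linear scales".

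**PK rules.** Protocol 13.8 names a linear trapezoid for AUC to the last quantifiable sample, the observed last concentration for AUCinf, non-linear regression for half-life, and a two-part condition for parameter summaries. SAP 4.9 and Table 26 name a linear-log trapezoid, the estimated last concentration, log-linear regression, and a minimum of three evaluable subjects. Protocol 13.8 leaves exact PK details to the SAP. SAP Section 5 reports no changes from the protocol's analyses and names pharmacokinetics explicitly.

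**The concern.** Each hour label contradicts the day count printed beside it, in the section that governs the PK analysis. A table or mean plot built on these labels would show the last two dose 12 concentrations a day earlier than they were taken. The 144 h label also coincides with the upper end of the window that the Table 26 footnote gives the 96 h sample (48 to 144 h), so two planned samples can appear to share a time.

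On the rules, two analysts working from the two documents would obtain different SAD AUClast values from the same concentrations. They could also disagree on whether a parameter may be summarised at all. A reader who relies on Section 5 would not know that there was anything to reconcile.

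**Working it through.** **1. Hour labels**

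Inputs: dose 12 at 600 h, the 24 h PK visit at 624 h, the 96 h PK visit at 696 h, the 7-day visit at 768 h and the 28-day visit at 1272 h (protocol Tables A.1-5 and A.1-6, repeated in SAP Appendix 1); Days 26, 33 and 54 (SAP Table 5).

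Reproducing the SAP figures: 144 and 648 result only when counting from the 24 h visit (768 − 624 = 144; 1272 − 624 = 648) or, equivalently, from one day too few (6 × 24 = 144; 27 × 24 = 648). Neither origin fits the rest of the list, which counts from dose 12: 624 − 600 = 24 and 696 − 600 = 96.

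Counting from dose 12:

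| Route | 7-day sample | 28-day sample |
|---|---|---|
| Days × 24 | 7 × 24 = 168 | 28 × 24 = 672 |
| Schedule clock | 768 − 600 = 168 | 1272 − 600 = 672 |
| Study days | (33 − 26) × 24 = 168 | (54 − 26) × 24 = 672 |
| SAP label | 144 | 648 |
| Shortfall | 24 h | 24 h |

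**2. PK rules side by side**

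| Item | Protocol 13.8 | SAP 4.9 / Table 26 |
|---|---|---|
| AUC to last quantifiable sample | linear trapezoid | linear-log trapezoid |
| Last concentration in AUCinf | observed | estimated |
| Parameter summaries | at least 50% evaluable and at least 3 values | at least 3 evaluable subjects |
| Terminal slope | non-linear regression | log-linear regression |

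The first three are direct replacements of a named rule. The fourth is also a difference in the named method.

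**3. Size of the AUC difference**

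The documents give no half-life and no LLQ, so this rests on assumptions: one compartment, first-order absorption with ka 0.5, 1, 2 or 4 per h, half-life 6, 12, 24 or 48 h, the SAD sampling times, and AUC taken to the last sample at or above the LLQ.

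| LLQ as share of Cmax | Linear AUClast above linear-log |
|---|---|
| 0 (all quantifiable) | 4.9% to 10.3% |
| 0.1% | 4.9% to 10.1% |
| 1% | 1.7% to 8.7% |
| 5% | 1.7% to 6.6% |
| 10% | 0.5% to 6.1% |

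The result depends on the half-life chosen. With all samples quantifiable, a 4 h half-life gives 12% to 13% and a 100 h half-life about 1.6%.

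**4. Evaluability threshold**

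With N treated active subjects as the denominator, the protocol requires max(3, N/2 rounded up) and the SAP requires 3.

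- N = 6 (planned): 6/2 = 3, so the rules coincide.
- N = 7 or 8 (for example after replacement under protocol 13.3.3): protocol 4, SAP 3.
- N = 9 (four subjects added under protocol 4.3, split 3:1, so 6 + 3): 9/2 = 4.5, so protocol 5, SAP 3.

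If the denominator is the PK Population instead, the gap may shrink or vanish, because SAP 4.9 removes non-evaluable subjects from that population. Neither document states the denominator.

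**The case against.** **The labels are a self-correcting slip.** The correct day count stands next to each wrong hour, sampling is tied to visits 7 and 28 days after the last dose, and protocol 7.1 has actual times recorded. SAP 4.9 itself lists concentrations and gives summary statistics only for parameters, so within the SAP the labels reach only the mean plots; the route to tables is protocol 13.8. All of this stands. It limits the effect but does not make the labels right.

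**A reader might infer that the dose 12 half-life is biased.** If the labels entered a log-linear fit of a mono-exponential decline through the 24 h, 96 h and 7-day points, the half-life would come out 15.6% too short with R-squared 0.987, which the SAP's 0.9 criterion would pass. The documents do not support treating this as an expected error. Nothing says that nominal times enter the fit, and the Table 26 footnote uses an observed 48 h value when the windowed sample falls there, which points to actual times. The late samples must also be quantifiable. With an LLQ at 1% of Cmax, log2(100) = 6.64 half-lives must cover the interval, so the half-life must be at least about 168/6.64 = 25 h for the 7-day sample and 672/6.64 = 101 h for the 28-day sample. What remains is that SAP 4.9 does not say which times are used.

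**Protocol 13.8 defers exact details to the SAP.** That permits detail where the protocol is silent. It does not make a no-changes statement true where the protocol names one method and the SAP another.

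**Version.** The SAP cites protocol versions 8.0 to 8.2, and the version supplied cannot be confirmed. Some schedule entries differ: SAP Table A.2-2 has an additional 24 h urine sample after dose 1. The rule comparison therefore holds against the supplied text only.

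**Conclusion.** The label error is certain: both dose 12 labels are 24 h short and should be 168 and 672 h. Its reach is nominal-time summaries and mean profile plots. No sample or visit moves, and parameters are affected only if nominal times are used.

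The rule differences are also plain, subject to the version caveat: at least three named rules differ, with the terminal-slope method as a fourth. On the supplied text the Section 5 statement is therefore incorrect. The AUC rules differ by about 0.5% to 10% for SAD AUClast under the stated model; this illustrates the size and is not a bound. The change from observed to estimated last concentration is a matter of disclosure. A reader might infer that the evaluability rules differ throughout, or only after a cohort is expanded. Neither is right: they coincide at the planned 6 active subjects and can diverge once a cohort exceeds 6, by expansion or by replacement, depending on the denominator.

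Severity is minor. PK is a secondary, descriptive objective, and the MTD rests on DLTs, not on exposure.

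**What to change.** In the SAP:

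- Section 4.9: replace 144 and 648 h with 168 and 672 h.
- State that PK parameters use actual sampling times and that nominal times serve summaries and plots only.
- Keep one AUC rule. Linear-log is a reasonable choice if it is disclosed.
- Keep one convention for the last concentration in AUCinf and one terminal-slope method.
- Keep one evaluability rule and state its denominator (treated subjects or PK Population).
- Section 5: list each departure from protocol 13.8 with a short reason, and name the protocol version against which it was checked.
- Table 26, editorial: write apparent volume as Dose/(AUC × λz) in both rows, since the present form can be read as multiplying by λz.

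The cost is wording only, with no new samples, visits or subjects.
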